6.1 Study Interventions Administration

Study Intervention Name:	Crinone®	Duphaston®
Dose Formulation:	Progesterone gel 8% (90 mg)	Tablet
Unit Dose Strength(s)/Dosage Level(s):	90 mg	10 mg/tablet
Route of Administration:	Intravaginal	Oral
Dosing Instructions:	1 gel, q.d. in the morning	1 tablet, b.i.d
Supplier/Manufacturer:	Merck will provide Crinone® for free	Prescribed for participants in the clinic by Investigators
Packaging and Labeling	
every box contains 15 applicatorsThe validity period is 36 monthsEach applicator will be packaged and labeled per all applicable regulatory requirements and Good Manufacturing Practice Guidelines.	
According to the package labelling as prescribed by the Investigator

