8.4 Study intervention Overdose

For this study, any dose of Crinone® greater than 90 mg/p.v./q.d in the single treatment group, or Crinone® at 90 mg/p.v./q.d and Duphasston® at 10 mg/p.o./b.i.d in the combination treatment group will be considered an overdose. The schedule can be seen in [Section 1.3](#). In case of an overdose, the participant will be assessed by Investigators as to whether they will continue participating in the study or not. Rescue medicines that are administered are not considered overdosing.

Even if it is not associated with an AE or a SAE, any overdose is recorded in the CRF and reported to drug safety in an expedited manner. Overdoses are reported on a SAE Report Form, following the procedure in [Appendix 3](#), section on Reporting Serious Adverse Events.

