- Study intervention A (Crinone® group): Randomized participants will be given Progesterone gel 8% (Crinone®) 90 mg/p.v./q.d from the day of endometrial transformation. It will be suggested that they administer the drug in the morning and at the same time of day throughout the trial. A β -hCG test will be done 14 days after ET. If serum β -hCG levels are negative, the study will be discontinued. If the result of the β -hCG test is positive, Crinone® administration will continue with the above regimen. At 35 days after ET, an ultrasound will be done to detect the number of gestational sacs to confirm the results of clinical pregnancy. If clinical pregnancy is positive, continue Crinone® administration until ongoing pregnancy assessment. Should a miscarriage occur at any point, Crinone® administration will be discontinued.
- Study intervention B (Crinone® + Duphaston® group): Randomized participants will be given Progesterone gel 8% (Crinone®) 90 mg/p.v./q.d from the day of endometrial transformation, following which Duphaston® at 10 mg/p.o./bid will be administered from the day of ET. It will be suggested that they administer the drugs in the morning and at the same time of day throughout the trial. A β -hCG test will be done 14 days after ET. If serum β -hCG levels are negative, the study will be discontinued. If the result of the β -hCG test is positive, the combination medication will continue with the above regimen. At 35 days after ET, an ultrasound will be done to detect the number of gestational sacs to confirm the results of clinical pregnancy. If clinical pregnancy is positive, continue combination medication until ongoing pregnancy assessment. Should a miscarriage occur at any point, combination medication will be discontinued.

All participants will receive oral estradiol valerate continuously and the dose of estradiol valerate will be adjusted according to local practices.

The following data will be collected:

- Duration and total dosage of estradiol valerate

- Date of ET
- Number of embryo(s) transferred (no more than 2)
- Embryo quality
- Check I/E criteria
- Recording of AEs
- Concomitant medications prescribed and reasons.

Visit 4 (β -hCG positive assessment)

Participants treated by ART are routinely monitored for early detection of pregnancy by measuring serum β -hCG concentration according to the site's routine clinical practices.

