### Compliance

- Compliance (%) = 100 \* actual dose/planned dose for study intervention duration.
  - Crinone Planned Dose: 90mg/gel, q.d
  - Duphaston Planned Dose: 10mg/tablet, b.i.d

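### Two combination-arm wordings need reconciling: the morning timing advice does not fit twice-daily Duphaston, and the overdose clause names the assigned regimen

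*Protocol*

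**What the plan says.** **Timing.** Protocol Section 6.1 gives Crinone as "1 gel, q.d. in the morning" and Duphaston as one tablet twice daily, with no time of day. Appendix 4, Visit 3, repeats the regimens by arm. For the Crinone-only arm the advice is "It will be suggested that they administer the drug in the morning and at the same time of day throughout the trial". For the combination arm, Duphaston is added: "following which Duphaston® at 10 mg/p.o./bid will be administered from the day of ET". The sentence that follows is "It will be suggested that they administer the drugs in the morning and at the same time of day throughout the trial".

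**Overdose.** Protocol Section 8.4 defines overdose for both arms in one sentence. The first limb is "any dose of Crinone® greater than 90 mg/p.v./q.d in the single treatment group". The second is "or Crinone® at 90 mg/p.v./q.d and Duphasston® at 10 mg/p.o./b.i.d in the combination treatment group will be considered an overdose". An overdose leads the investigator to assess whether the participant continues. It is recorded in the CRF and sent to drug safety as an expedited report on an SAE form, even when no adverse event accompanies it. Rescue medicines are exempt.

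**SAP.** Section 13 uses the same regimen for compliance: "Duphaston Planned Dose: 10mg/tablet, b.i.d".

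**The concern.** A single morning time suits a once-daily gel. It does not suit a tablet taken twice a day, and nothing in Appendix 4 mentions a second time. A participant or nurse who takes the sentence at face value has no guidance on the second tablet. Section 6.1 does not create this problem, because there the morning belongs to Crinone only.

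The overdose sentence matters more, because it triggers an action. Only its first limb says that the dose must be exceeded. The second limb describes what a combination-arm participant is meant to take. A site has to supply the missing condition, and then has to decide whether one drug or both must be exceeded. The two arms could then be held to different reporting rules for the same event, in an open-label study that has comparative safety among its secondary objectives.

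**Working it through.** There is no planned figure to reproduce. The check sets the passages side by side and applies each reading of the overdose sentence to the possible cases.

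**Step 1: is the Duphaston regimen itself consistent?**

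- Protocol 6.1: one 10 mg tablet twice daily.
- Protocol 8.4: 10 mg twice daily.
- Protocol Appendix 4, Visit 3: 10 mg twice daily.
- SAP Section 13: 10 mg tablet, twice daily.
- Protocol 2.2 and 4.3: 20 mg.

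10 mg × 2 = 20 mg a day, so all five agree. Amount and frequency are not in dispute.

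**Step 2: does the timing advice fit?**

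| | Crinone (once daily) | Duphaston (twice daily) |
|---|---|---|
| Section 6.1 | morning | no time stated |
| Appendix 4, Crinone-only arm | morning, same time | not given |
| Appendix 4, combination arm | morning, same time | morning, same time |

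Only the bottom right cell fails to fit the frequency in its column heading. The sentences for the two arms are the same apart from *drug* and *drugs*, which suggests that the text was carried over.

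**Step 3: how does the overdose sentence classify each case?**

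Three readings of the combination limb are possible:

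- *Literal*: as printed, taking the named doses is an overdose.
- *Either*: the exceeding condition is carried over, and exceeding one drug suffices.
- *Both*: the exceeding condition is carried over, and both drugs must be exceeded.

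All cases exclude rescue use.

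| Case | Crinone-only arm | Combination, literal | Combination, either | Combination, both |
|---|---|---|---|---|
| Assigned regimen | no | **yes** | no | no |
| Crinone exceeded only | yes | not named | yes | **no** |
| Duphaston exceeded only | not applicable | not named | yes | no |
| Both exceeded | not applicable | not named | yes | yes |

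The literal reading captures women who take exactly what they were assigned. The *both* reading reports a Crinone excess in one arm and not the same excess in the other. Only the *either* reading treats a Crinone excess alike in the two arms, and the text does not select it.

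**Step 4: does this reach the planned analyses?** The primary analysis is by assigned arm and uses neither timing nor overdose status. SAP Section 15 plans no overdose table. The effect is on participant advice, CRF overdose records, expedited SAE-form reports and the decision on continuing.

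**The case against.** The strongest reply is that both items are drafting slips that a competent site would read through. The timing is a suggestion, and it directly follows the twice-daily frequency without replacing it. It can be read as consistent clock times starting in the morning. Duphaston comes on an investigator's prescription and is labelled accordingly, and Appendix 4 procedures follow the site's routine practice. In Section 8.4, under a heading about overdose, carrying the exceeding condition into the second limb is the natural reading. Most of this stands, and it limits the weight of the point. It does not settle whether *and* means either drug or both, and it does not make the Appendix 4 sentence agree with Section 6.1.

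A reader might infer more than the documents support:

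- **That the combination dosing contradicts itself.** It does not; Step 1 shows one amount and one frequency throughout.
- **That the whole combination arm, 334 / 2 = 167 women, would be reported as overdosed.** That rests on a literal reading that is plainly not the intent.
- **That half the planned Duphaston would be lost.** One tablet a day would give 10/20 = 50% compliance, below the 80% minimum in Section 6.4, and both tablets together would give 20/20 = 100%. The documents do not show that women would do either. Nor do SAP Sections 8.1 and 8.2 name compliance below 80% as a ground for exclusion from the per-protocol population. A count of 63 of 126 tablets would apply only to women treated to Day 63; those with a negative β-hCG test stop at about Day 14.
- **That the trial's contrast changes.** No such effect is shown.

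**Conclusion.** The point holds as a matter of wording in two operative passages. The combination-arm timing advice in Appendix 4 does not fit the Duphaston frequency given just before it, or Section 6.1. The combination limb of Section 8.4 is wrong as printed. With its probable intent supplied, it is still unclear whether exceeding one drug is enough.

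The practical consequence is possible unequal reporting between arms: under one of the two sensible readings, an identical Crinone excess is an overdose in the Crinone-only arm and not in the combination arm. The documents give no expected overdose frequency, so the number of affected reports cannot be estimated. No effect on the primary analysis or the planned number of participants is claimed. The conclusion assumes that sites apply Section 8.4 from its text and that no other trial document already clarifies it. It takes no view on which dose, time or threshold is clinically right.

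**What to change.** 1. Reconcile Appendix 4, Visit 3, combination arm, with Section 6.1. State the timing advice separately for each drug, in line with the frequency already given for that drug.
2. Restate Section 8.4 per drug and in the same form for both arms, so that the assigned regimen falls outside the definition and the joining *and* no longer has to be interpreted.

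The sponsor and investigator set the clinical values in both places. The cost is a few sentences in a protocol amendment, with the IRB/IEC approval that Appendix 2 requires. No new procedure, participant diary, data item or change to the SAP compliance derivation is needed: neither document mentions a diary or shows that individual dosing occasions are recorded, and the wording can be put right without them.

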**2 List of Abbreviations and Definition of Terms**

ADaM	Analysis Data Model
AE	Adverse event
ATC	Anatomical Therapeutic Chemical classification
CI	Confidence Interval
(e)CRF	(electronic) Case Report Form
CSR	Clinical Study Report
EDC	Electronic data capture
ET	Embryo transfer
FET	Frozen-thawed embryo transfer
β-hCG	Beta human chorionic gonadotrophin
IAP	Integrated Analysis Plan
ICH	International Council for Harmonization
ITT	Intention-to-treat
IVRS	Interactive Voice Response System
LOCF	Last Observation Carried Forward
MedDRA	Medical Dictionary for Regulatory Activities
NA	Not Applicable
PD	Protocol Deviation
PT	Preferred Term
PP	Per protocol
SAE	Serious adverse event
SCR	Screening analysis population
SD	Standard Deviation
SOC	System Organ Class
TEAE	Treatment-Emergent Adverse Event
TLF	Tables, Listings, and Figures
WHO-DD	World Health Organization Drug Dictionary
MedDRA	Medical Dictionary for Regulatory Activities

### 3 Modification History

Unique Identifier for Version	Date of IAP Version	Author	Changes from the Previous Version
1.0	26 April 2019	PPD	new

### 4 Purpose of the Integrated Analysis Plan

The purpose of this IAP is to document technical and detailed specifications for the final analysis of data collected for protocol MS200113\_0005. Results of the analyses described in this IAP will be included in the Clinical Study Report (CSR). Additionally, the planned analyses identified in this IAP will be included in future manuscripts. Any post-hoc, or unplanned analyses performed to provide results for inclusion in the CSR but not identified in this prospective IAP will be clearly identified in the CSR.

The IAP is based upon section 9 (Statistical Consideration) of the study protocol and is prepared in compliance with ICH E9. It describes analyses planned in the protocol.

The first version (version 1.0) focused on the detailed description of the planned explorative analyses of efficacy and safety variables.

### 5 Objectives and Endpoints

Objectives	Endpoints (Outcome Measures)	Endpoints (Outcome Measures) Timeframe	IAP section
Primary			
To investigate the ongoing pregnancy rate of Crinone® compared to Crinone® in combination with Duphaston® during artificial FET cycles in Chinese population.	Ongoing pregnancy	At 10-12 weeks of pregnancy [8-10 weeks after ET]	14.1
Secondary			
To evaluate the efficacy of Crinone® compared to Crinone® in combination with Duphaston® for luteal phase support in artificial FET cycles.	

• β-hCG positive

	At 4 weeks of pregnancy [2 weeks after ET]	14.2
	

• Implantation

• Clinical pregnancy

	At 6-8 weeks of pregnancy [4-6 weeks after ET]	14.2

Objectives	Endpoints (Outcome Measures)	Endpoints (Outcome Measures) Timeframe	IAP section
To evaluate the safety of Crinone® compared to Crinone® in combination with Duphaston® for luteal phase support in artificial FET cycles.	• Early abortion	Time from ET to 12 weeks of pregnancy	14.2
	• Luteal phase bleeding	Time from ET to β-hCG positive assessment	15.2.3
	• Vaginal bleeding	Time after β-hCG positive assessment	15.2.3
	• The safety profile of the study intervention	Time from the first day of study intervention after randomization to last dose of study intervention date or the clinical cut-off date, whatever occurs earlier.	15

## 6 Overview of Planned Analyses

No formal interim analyses are planned.

### Cut-off date

The final planned analysis identified in the Clinical Study Protocol and in this IAP will be performed only after the last subject has completed the study with all study data in-house, all data queries resolved, and the database locked.

## 7 Changes to the Planned Analyses in the Clinical Study Protocol

Protocol	IAP	
Original	Change	Rationale
• The CI for the difference between the two treatment groups will be calculated with the Pearson chi-square test	The CI for the difference between the two treatment groups will be calculated with the stratified "Miettinen-Nurminen" method	There is stratification randomization in this study, previous proposed Pearson chi-square test cannot provide the CI for stratified data, thus calculation method was changed to be stratified "Miettinen-Nurminen" method
• Early abortion was listed as safety secondary endpoint in the synopsis.	Early abortion is listed in the efficacy secondary endpoint section	Early abortion is a failure to pregnancy, so move it under the efficacy endpoint.

## 8 Protocol Deviations and Analysis Populations

### 8.1 Definition of Protocol Deviations

Important protocol deviations are protocol deviations that might significantly affect the completeness, accuracy, and/or reliability of the study data or that might significantly affect a subject's rights, safety, or well-being.

The following deviations will be identified and confirmed prior to or at the Data Review Meeting at the latest.

Important protocol deviations include:

- Deviations from the inclusion and exclusion criteria
- Deviations post inclusion
- Subset of these important protocol deviations are clinically important, if leading to the exclusion of a subject from an analysis population (see section 8.2)

All important protocol deviations based on eCRF database are documented in ADaM datasets whether identified through site monitoring, medical review or programming.

### 8.2 Definition of Analysis Populations and Subgroups

The analysis populations are specified below. The final decision to exclude subjects from any analysis population will be made during a data review meeting prior to database lock.

Analysis Population	Description
Intention-to-Treat (ITT) Population	The ITT Population will include all subjects who receive at least one dose of randomized study intervention after randomization. Subjects will be analyzed according to the study intervention they were initially assigned.
Per-Protocol (PP) Population	Includes all subjects in ITT population without any important protocol violations.
Safety Population	Include all subjects who have received at least one dose of study intervention after randomization. Subjects will be analyzed according to the actual study intervention they received.

The general use of the analysis populations in the different analyses are summarized as below.

Analyses	Analysis Population		
	Intent-to-Treat	Per Protocol	Safety
Baseline Assessments	✓		
Concomitant Therapies	✓		
Compliance and Exposure			✓

Analyses	Analysis Population		
	Intent-to-Treat	Per Protocol	Safety
Efficacy: Primary	✓	✓	
Efficacy: Secondary	✓	✓	
Safety			✓

If the Per Protocol analysis population includes at least 90% of subjects in the ITT analysis population, additional efficacy analyses on the Per Protocol analysis population will be omitted as the differences in the results based upon these two analysis populations are expected to be negligible.

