6.4 Study Intervention Compliance

See [Section 6.2](#) for dispensing and accountability of the study interventions.

Crinone® will be provided for free and Duphaston® will be prescribed by the physicians and will be bought by the participants themselves. Study intervention administration must be recorded in the CRF as applicable.

The acceptable compliance for this study is at a minimum of 80%.

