## **9 General Specifications for Data Analyses**

### **Study intervention groups**

Study intervention groups are defined and labelled as Crinone® and combination medication (Crinone® plus Duphaston®).

Unless otherwise indicated all analyses will be presented separately for the two study intervention groups.

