## **10 Study Subjects**

The subsections in this section include specifications for reporting subject disposition and study intervention/study discontinuations. Additionally, procedures for reporting protocol deviations are provided.

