### **10.1 Disposition of Subjects and Discontinuations**

- Total number of subjects screened (i.e. subjects who gave informed consent)
- Number of subjects who discontinued from the study prior to randomization overall and grouped by the main reason (e.g. the failed specific inclusion or exclusion criteria, withdraw of consent)
- Number of randomized subjects.
- Number of randomized subjects who received at least one dose of study intervention after randomization
- Number of randomized subjects who completed study after randomization, grouped by study intervention group and main reason.
- Number of randomized subjects who discontinued the study after randomization, grouped by study intervention group and main reason

The number and percentage of subjects in each of the above disposition categories will be presented by randomized study intervention group (if applicable) and overall. Percentages will be presented with respect to the number of randomized subjects. Study completion or discontinuation and their corresponding reasons will be summarized from “Study Termination” eCRF page.

Disposition of subjects by allocated study intervention group will be presented in a CONSORT Flow Diagram.

The results of the randomization algorithm (according to IVRS) will be summarized as follows:

- Number of subjects by randomization stratum (IVRS)

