### Analysis Population to be used for summaries:

- Safety population

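### Compliance is tabulated only on the as-treated Safety population, so the planned table can overstate adherence to Duphaston, the one drug that separates the arms

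*SAP*

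**What the plan says.** The table in SAP 8.2 that links analyses to populations ticks the row "Compliance and Exposure" under Safety only. SAP 13 repeats this: under "Analysis Population to be used for summaries" the single entry is "Safety population". A woman enters that population with one post-randomisation dose of study intervention, and either drug counts. Grouping is as treated: "Subjects will be analyzed according to the actual study intervention they received".

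SAP 9 defines two groups, Crinone and Crinone plus Duphaston, and states: "Unless otherwise indicated all analyses will be presented separately for the two study intervention groups".

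Protocol Appendix 4 (Visit 3) gives Crinone to both arms at the same planned dose and adds Duphaston from transfer day in the combination arm only. Under Protocol 6.4 Crinone is free, whereas Duphaston "will be prescribed by the physicians and will be bought by the participants themselves".

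SAP 13 defines compliance as actual dose over planned dose, as a percentage, for the duration of the intervention. It counts from the first dose after randomisation. The disposition list in SAP 10.1 includes "Number of randomized subjects who received at least one dose of study intervention after randomization", with no split by drug.

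**The concern.** As-treated grouping is the usual choice for adverse events. It suits compliance poorly, because compliance asks how far women followed what they were assigned. Here the mismatch has a particular effect. The combination is the comparator plus one drug, so failing to start that drug turns a combination-arm woman into someone who received exactly the comparator. Self-purchase in an open-label trial makes not starting a realistic departure from assignment, although the documents do not say that it is common.

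Protocol 2.2 asks whether the small oral dose is needed at all, and Protocol 9.4.3 says the result will inform later trials. A reader who sees a small difference in ongoing pregnancy will turn to the compliance table to judge whether Duphaston was actually taken. If that table covers starters only, it cannot answer the question, and a small difference could be taken too readily as evidence that Duphaston adds nothing.

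**Working it through.** The plan states no expected compliance or non-start rate, so there is no figure of its own to reproduce. The check has two parts.

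**1. Applying the rules to one woman.** Take a woman randomised to the combination who uses Crinone after randomisation and takes no Duphaston.

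- Safety population: she qualifies through her Crinone dose.
- Group: what she received is Crinone alone, one of the only two labels in SAP 9. On a plain reading she sits in the Crinone column.
- Duphaston compliance: that column has no planned Duphaston, so no Duphaston value is computed for her. The combination column holds only women who took some.
- If a programmer keeps her under the combination instead: she has no first Duphaston dose, so the start-date rule in SAP 13 gives her no Duphaston period. Her value could be set to missing. Nothing written makes it 0%.
- Disposition: the at-least-one-dose row in SAP 10.1 counts her, again because of Crinone.

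**2. Size under stated assumptions.**

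Inputs from the documents: 334 participants (Protocol 4.1) and 1:1 allocation (Protocol 6.3.1), so 334 / 2 = 167 per arm.

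Assumptions, not in the documents: k combination-arm women never start Duphaston, for about 1% to 15% of the arm; mean Duphaston compliance among starters is c = 95%; every woman takes at least one post-randomisation Crinone dose; there is no other crossover.

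Formulas:
- as-treated mean = c, on 167 − k women
- mean by assigned arm, non-starters at 0% = c × (167 − k) / 167, on 167 women
- gap = c × k / 167

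| Assumed share | k | As-treated mean (n) | Mean by assigned arm (n = 167) | Gap, points | Crinone column n |
|---|---|---|---|---|---|
| 1% | 2 | 95.0% (165) | 95 × 165/167 = 93.9% | 1.1 | 169 |
| 2% | 3 | 95.0% (164) | 95 × 164/167 = 93.3% | 1.7 | 170 |
| 5% | 8 | 95.0% (159) | 95 × 159/167 = 90.4% | 4.6 | 175 |
| 10% | 17 | 95.0% (150) | 95 × 150/167 = 85.3% | 9.7 | 184 |
| 15% | 25 | 95.0% (142) | 95 × 142/167 = 80.8% | 14.2 | 192 |

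Varying c from 90% to 100% over the same values of k, the gap runs from 90 × 2/167 = 1.1 to 100 × 25/167 = 15.0 points. It is zero only if every woman starts. The as-treated mean does not move with k, so the table carries no information about non-starting.

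**The case against.** Compliance and exposure on a Safety set is a common and defensible choice, and several stronger readings go further than the documents allow.

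- **That the SAP certainly moves the woman to the Crinone group.** It does not say so. Receipt of only one of two components is undefined, and she could be kept under the combination. This stands: the point rests on a plain reading plus a gap in definition. Keeping her there does not by itself bring her 0% into the mean.
- **That her Crinone compliance would be judged against the wrong plan.** It would not. The planned Crinone dose is the same in both arms.
- **That the table would report everyone as meeting the 80% minimum.** That minimum appears in Protocol 6.4 only. SAP 13 plans no tabulation against it.
- **That non-starters would be invisible everywhere.** They might not be. Safety columns of 159 and 175 beside 167 randomised per arm would prompt questions. SAP 8.1 includes post-inclusion deviations that could affect data reliability, and SAP 10.2 tabulates and lists these together with reasons for per-protocol exclusion. However, neither never starting Duphaston nor low compliance is named there, and none of these outputs is a compliance result.
- **That the missing drug-discontinuation rows belong to the same defect.** SAP 10 promises "specifications for reporting subject disposition and study intervention/study discontinuations", while SAP 10.1 lists study discontinuations only. Those rows would concern women who start and then stop, which is a separate matter from as-treated grouping. SAP 15.1.2 covers stopping Duphaston because of an adverse event.

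It is also fair to say that self-purchase makes non-starting possible without showing it to be frequent. At the low end of the assumed range the gap is about one point.

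**Conclusion.** The point holds as a weakness in the compliance table. As planned, that table can describe Duphaston adherence among starters only, and the SAP leaves the classification of a partly taken combination open. With 167 per arm and an assumed 95% mean among starters, the overstatement is 1.1 points at about 1% non-starters and 14.2 points at about 15%. The true rate is unknown, so the size cannot be pinned down further.

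A reader might infer that the primary result is therefore wrong. The documents do not support that. Efficacy is analysed by assigned arm, compliance feeds no calculation in SAP 14, and no confirmatory test is planned. Any dilution of the ITT contrast by non-starters would be the same whichever population is used for compliance. What suffers is the reader's ability to interpret the estimate. This is a reporting change worth making before database lock.

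**What to change.** 1. In the SAP 8.2 table and in SAP 13, tabulate compliance separately for each drug, by randomised arm, on all randomised women. Moving it to the ITT population as worded may not be enough. SAP 8.2 admits to ITT only women with a dose of the randomised intervention, which could be read to exclude a combination-arm woman who took no Duphaston.
2. State in SAP 13 that a combination-arm woman with no Duphaston record counts as 0% for Duphaston, by rule, so that the absence of a first dose does not make her missing.
3. Split the at-least-one-dose row in SAP 10.1 into Crinone and Duphaston by randomised group, so that the number of non-starters is shown.
4. State in SAP 8.2 how a woman who takes only part of the combination is classified as treated. Keep as-treated grouping for adverse events and safety exposure.

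The Duphaston administration eCRF page cited in SAP 13 already supplies the data. The cost is SAP wording and one or two extra table rows. Reported compliance may look less favourable.
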